6.3.2 Investigator Global Assessment

The IGA is an Investigator--lead assessment scale used to determine severity of AD and clinical response to treatment. It is based on a 5-point scale, ranging from 0 (clear) to 4 (severe). A copy of the IGA is also included in Section 17.3 (Appendix 3).

This assessment will be completed using an internet-enabled device.

6.3.3 SCORing of Atopic Dermatitis Index

The SCORAD Index is a validated clinical tool that was developed to standardise the evaluation of the extent and severity of AD [SCORAD Dermatol Basel Switz 1993]. A copy of the SCORAD Index is included in Section 17.4 (Appendix 4). This assessment will be completed using an internet-enabled device.

To determine the extent of AD, the affected area (A) as a percentage of the whole body is determined, with a maximum score of 100% (head and neck [9%], upper limbs [9% each], lower limbs [18% each], anterior trunk [18%], back [18%], genitals [1%]). The severity (B) of 6 specific symptoms of AD (redness, swelling, oozing/crusting, scratch marks, skin thickening [lichenification], dryness [area where there is no inflammation]) is assessed on a 4-point scale, with a maximum score of 18: none (0), mild (1), moderate (2) or severe (3). Subjective symptoms (ie, itch and sleeplessness; C) are recorded as scored by the patient or relative on a visual analogue scale (VAS), where 0 is no itch (or sleeplessness) and 10 is the worst imaginable itch (or sleeplessness), with a maximum possible score of 20.

The SCORAD score for each patient is calculated as: A/5 + 7B/2 + C.

6.3.4 Body Surface Area Involvement of Atopic Dermatitis

Body surface area (BSA) affected by AD will be assessed for each section of the body (the possible highest score for each region is: head and neck [9%], anterior trunk [18%], back [18%], upper limbs [18%], lower limbs [36%], and genitals [1%]) and will be reported as a percentage of all major body sections combined.

6.3.5 Patient Oriented Eczema Measure

The POEM is a tool used for monitoring atopic eczema severity. It focuses on the illness as experienced by the patient. This will be completed using an internet-enabled device. A copy of the POEM form is included in Section 17.5 (Appendix 5). The questionnaire consists of 7 questions pertaining to the symptoms of AD and their frequency. Scores are based on a scale of zero (no days) to 4 (every day in the last week) for each question, with a maximum score of 28 possible for all questions. A POEM total score is correlated to eczema severity (0-2 [clear or almost clear], 3-7 [mild], 8-16 [moderate], 17-24 [severe], 25-28 [very severe]).

6.3.6 Dermatology Life Quality Index

The DLQI is a dermatology-specific QoL instrument and is a simple, validated questionnaire. A copy of the DLQI is included in Section 17.6 (Appendix 6). This will be completed using an internet-enabled device.

The instrument consists of 10 questions pertaining to the effect of AD on QoL. Scores are based on a scale of "0" (not at all/not relevant/question unanswered) to "3" (very much/prevented work or studying), with a maximum score of 30 possible for all questions. The total score is correlated to the detrimental effect of AD on QoL (0-1 [no effect at all on patient's life], 2-5 [small effect], 6-10 [moderate effect], 11-20 [very large effect] and 21-30 [extremely large effect]).

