17.5 Appendix 5 - Patient Oriented Eczema Measure

UNITED KINGDOM · CHINA · MALAYSIA

POEM for self-completion

Please circle one response for each of the seven questions below about your eczema. Please leave blank any questions you feel unable to answer.

1. Over the last week, on how many days has your skin been itchy because of your eczema?

No days 1-2 days 3-4 days 5-6 days Every day

2. Over the last week, on how many nights has your sleep been disturbed because of your eczema?

No days 1-2 days 3-4 days 5-6 days Every day

3. Over the last week, on how many days has your skin been bleeding because of your eczema?

No days 1-2 days 3-4 days 5-6 days Every day

4. Over the last week, on how many days has your skin been weeping or oozing clear fluid because of your eczema?

No days 1-2 days 3-4 days 5-6 days Every day

5. Over the last week, on how many days has your skin been cracked because of your eczema?

No days 1-2 days 3-4 days 5-6 days Every day

6. Over the last week, on how many days has your skin been flaking off because of your eczema?

[figure not shown]
No days 1-2 days 3-4 days 5-6 days Every day

7. Over the last week, on how many days has your skin felt dry or rough because of your eczema?

No days 1-2 days 3-4 days 5-6 days Every day

Total POEM Score (Maximum 28):

© The University of Nottingham _____

UNITED KINGDOM · CHINA · MALAYSIA

POEM for self-completion

How is the scoring done?

Each of the seven questions carries equal weight and is scored from 0 to 4 as follows:

No days = 0 1-2 days = 1 3-4 days = 2 5-6 days = 3 Every day = 4

Note:

- If one question is left unanswered this is scored 0 and the scores are summed and expressed as usual out of a maximum of 28
- If two or more questions are left unanswered the questionnaire is not scored
- If two or more response options are selected, the response option with the highest score should be recorded

References

Charman CR, Venn AJ, Williams HC. The Patient-Oriented Eczema Measure: Development and Initial Validation of a New Tool for Measuring Atopic Eczema Severity From the Patients' Perspective.

Arch Dermatol. 2004;140:1513-1519

© The University of Nottingham

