17.6 Appendix 6 - Dermatology Quality of Life Index

The aim of this questionnaire is to measure how much your skin problem has affected your life OVER THE LAST WEEK. Please tick ☑ one box for each question.

1.	Over the last week, how itchy , sore , painful or stinging has your skin been?	Very much A lot A little Not at all	
2.	Over the last week, how embarrassed or self conscious have you been because of your skin?	Very much A lot A little Not at all	
3.	Over the last week, how much has your skin interfered with you going shopping or looking after your home or garden ?	Very much A lot A little Not at all	Not relevant 🗖
4.	Over the last week, how much has your skin influenced the clothes you wear?	Very much A lot A little Not at all	Not relevant □
5.	Over the last week, how much has your skin affected any social or leisure activities?	Very much A lot A little Not at all	Not relevant □
6.	Over the last week, how much has your skin made it difficult for you to do any sport ?	Very much A lot A little Not at all	Not relevant □
7.	Over the last week, has your skin prevented you from working or studying ?	Yes No	Not relevant □
	If "No", over the last week how much has your skin been a problem at work or studying?	A lot A little Not at all	
8.	Over the last week, how much has your skin created problems with your partner or any of your close friends or relatives ?	Very much A lot A little Not at all	Not relevant □
9.	Over the last week, how much has your skin caused any sexual difficulties ?	Very much A lot A little Not at all	Not relevant □
10.	Over the last week, how much of a problem has the treatment for your skin been, for example by making your home messy, or by taking up time?	Very much A lot A little Not at all	Not relevant □

Please check you have answered EVERY question. Thank you.

Property of the Sanofi Group - strictly confidential

PAGE 136 OF 147

[©]AY Finlay, GK Khan, April 1992 www.dermatology.org.uk, this must not be copied without the permission of the authors.

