### 8.3 Analysis of Other Secondary Efficacy Endpoints

Below are the additional other secondary efficacy endpoints for the study:

- Absolute change from baseline in EASI at Days 15 (Week 2), 29 (Week 4), 57 (Week 8), 85 (Week 12), 113 (Week 16), 141 (Week 20) and 169 (Week 24).
- Percentage change from baseline in EASI at Days 15 (Week 2); 29 (Week 4), 57 (Week 8), 85 (Week 12) and 141 (Week 20).
- Percentage of patients with at least a 50% reduction from baseline in EASI (EASI 50) at Days 15 (Week 2), 29 (Week 4), 57 (Week 8), 85 (Week 12), 113 (Week 16), 141 (Week 20) and 169 (Week 24).
- Percentage of patients with at least a 75% reduction from baseline in EASI (EASI 75) at Days 15 (Week 2), 29 (Week 4), 57 (Week 8), 85 (Week 12) and 141 (Week 20).
- Percentage of patients with at least a 90% reduction from baseline in EASI (EASI 90) at Days 15 (Week 2), 29 (Week 4), 57 (Week 8), 85 (Week 12), 113 (Week 16), 141 (Week 20) and 169 (Week 24).
- Percentage of patients with a 100% reduction from baseline in EASI (EASI 100) at Days 15 (Week 2), 29 (Week 4), 57 (Week 8), 85 (Week 12), 113 (Week 16), 141 (Week 20) and 169 (Week 24).
- Change in IGA from baseline to Day 169 (Week 24) and over time.
- Percentage of patients with a response of IGA 0 or 1 and a reduction from Baseline of  $\geq 2$  points at Days 15 (Week 2), 29 (Week 4), 57 (Week 8), 85 (Week 12) and 141 (Week 20).
- Absolute and percentage change in SCORAD Index from baseline to Day 169 (Week 24) and over time.
- Absolute and Percentage change in affected BSA from baseline to Day 169 (Week 24) and over time.
- Absolute and Percentage change in POEM from baseline to Day 169 (Week 24) and over time.
- Absolute and Percentage change in DLQI from baseline to Day 169 (Week 24) and over time.
- Absolute and Percentage change in ADCT from baseline to Day 169 (Week 24) and over time.
- Absolute and Percentage change in HADS from baseline to Day 169 (Week 24) and over time.
- Absolute and Percentage change in weekly average of pruritus NRS from baseline to Day 169 (Week 24) and over time.

- Proportion of patients with improvement (reduction) of weekly average of pruritus NRS  $\geq 3$  with a baseline pruritus NRS of  $\geq 3$  from baseline to Days 113 (Week 16) and 169 (Week 24).
- Time to loss of EASI 75 in patients randomized to withdrawal post-Week 24.
- Time to loss of IGA 0/1 in patients randomized to withdrawal post-Week 24.

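### DLQI items left unanswered score 0 with no stated limit on blanks, so a form with several blanks gets a total that is too low instead of being set to missing

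*Protocol*

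**What the plan says.** Protocol 6.3.6 and SAP 4.4.8 (item 7) describe DLQI scoring in the same terms. "The instrument consists of 10 questions pertaining to the effect of AD on QoL"; each is scored from 0 to 3, "with a maximum score of 30 possible for all questions". The score 0 covers three different situations: "not at all/not relevant/question unanswered". Lower is better; the bands begin "0-1 [no effect at all on patient's life], 2-5 [small effect], 6-10 [moderate effect".

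Neither section gives a maximum number of blanks, a minimum number of answered items, or a rule for an unscorable form. Protocol Appendix 6 prints the questionnaire without scoring rules and ends with a prompt to the patient: "Please check you have answered EVERY question".

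For POEM, Protocol Appendix 5 does print a limit. For a single blank: "If one question is left unanswered this is scored 0 and the scores are summed and expressed as usual out of a maximum of 28". Beyond that: "If two or more questions are left unanswered the questionnaire is not scored".

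The affected endpoint is listed in SAP 8.3 among the other secondary endpoints: "Absolute and Percentage change in DLQI from baseline to Day 169 (Week 24) and over time". For this group of endpoints the SAP provides mean differences with 95% confidence intervals and p-values at visits up to Week 24.

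**The concern.** A blank is missing information, yet the scoring rule gives it the same value as an answer that the skin had no effect. Items 3 to 10 have a separate box for not relevant, so a patient to whom such an item does not apply can say so. Items 1 and 2 have no such box, so a blank there cannot stand for not relevant, and it still scores 0.

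Because a partly completed form always yields a number, it would enter the analysis as an observed value. A rule for missing totals would not reach it. Elsewhere the plan recognises that too little data should not produce a score: POEM has its limit, and the baseline weekly pruritus NRS needs at least 4 of 7 daily scores.

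At stake is the accuracy of the DLQI changes at each scheduled visit, and of the comparison between arms if completeness differs between them.

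**Working it through.** **Inputs.** 10 items, item scores 0 to 3, blank = 0 (Protocol 6.3.6; SAP 4.4.8). Severity bands from the same sections. Change C_t = M_t − M_B and percentage change P_t = 100 × C_t / M_B (SAP 4). Item scores and the frequency of blanks are assumptions, because the documents give none.

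**1. The plan's own figure.** 10 × 3 = 30, which matches the stated maximum.

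**2. One form.** With every item at the same score v and b blanks, the total is v × (10 − b), so each blank removes 1/10 = 10%.

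| Item score v | 0 blanks | 2 blanks | 5 blanks | 10 blanks |
|---|---|---|---|---|
| 1 | 10 | 8 | 5 | 0 |
| 2 | 20 | 16 | 10 | 0 |
| 3 | 30 | 24 | 15 | 0 |

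At v = 2, five blanks move the patient from the band for a very large effect (11–20) to that for a moderate effect (6–10) with no real change. When item scores differ, one blank costs between 0 and 3 points, depending on what the skipped item would have scored.

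**3. Direction.** Take a true baseline of 20 (all items 2) and a true later total of 10 (all items 1).

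| Blanks | M_B | M_t | C_t | P_t |
|---|---|---|---|---|
| None | 20 | 10 | −10 | −50% |
| Two, later visit only | 20 | 8 | −12 | −60% |
| Two, baseline only | 16 | 10 | −6 | −37.5% |
| Two at both visits | 16 | 8 | −8 | −50% |

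Later blanks exaggerate improvement and baseline blanks shrink it. Blanks at both visits leave the percentage unchanged in this example but shrink the absolute change.

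**4. Arm mean at a visit.** If a share q of forms has b blanks and the mean item score is 1.5 (assumed), the mean total falls by q × b × 1.5.

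- b = 2: 0.05 × 2 × 1.5 = 0.15 up to 0.20 × 2 × 1.5 = 0.6 points.
- b = 5: 0.05 × 5 × 1.5 = 0.375 up to 0.20 × 5 × 1.5 = 1.5 points.

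These are shifts in one arm's mean. Equal shifts in both arms cancel in the difference between arms.

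**5. With a limit of one blank.** The largest understatement on a scored form is 3 of 30 points (one item that would have scored 3). Without a limit it is 30 of 30.

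**The case against.** **Direction.** A reader might infer that missing answers are systematically turned into benefit. The documents do not support that. The endpoint is change from baseline, the rule applies at every visit, and step 3 shows that baseline blanks work the other way. Nor is there support for a bias in favour of the drug: the trial is double-blind, and nothing in the documents suggests that completion would differ by arm.

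**The fully blank form.** A reader might also infer that an empty questionnaire would be analysed as the best possible score. That is the literal end point of the rule, but the text describes how responses are scored. An empty form may well be handled as an assessment not done, and nothing readable says it would be entered as 0. The point concerns partly completed forms.

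**The POEM comparison.** The POEM limit stands only on the scoring page reproduced in Appendix 5; the POEM descriptions in Protocol 6.3.5 and SAP 4.4.8 have none. The contrast may reflect which instrument pages were attached. So it does not show that the sponsor decided to leave the DLQI without a limit, and it does not by itself justify the same threshold for a ten-item form. This stands, and it is why the threshold needs confirming. The DLQI differs, however, in that the body text does state a rule for blanks, and that rule has no limit.

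**Redacted text.** Protocol 10.4.5 and parts of SAP 8.3 are blacked out, so a general rule there cannot be excluded. It is unlikely to close the gap: a missing-data rule acts on totals recorded as missing, and a form with several blanks has a total. The DLQI scoring paragraphs themselves show no redaction.

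**Exposure.** The form is electronic, patients review their eDiary with site staff (Protocol 6.3), and the form asks for every question to be answered. Few incomplete forms are likely. This stands and limits the importance of the point.

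**Conclusion.** The point holds as a minor one. Both documents state a rule that turns a largely incomplete DLQI form into a numeric total, and that total is too low whenever a skipped item would have scored above 0. Under equal item scores the error is 10% of the total per blank. On the assumed 5–20% of forms with two blanks and a mean item score of 1.5, one arm's mean at a visit would fall by 0.15 to 0.6 points on a 30-point scale.

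The net direction for change from baseline is unknown. The number of such forms is also unknown and probably small, and the device may require every answer, although neither document says so. A difference in completeness between arms would be needed to bias the comparison; without one, the effect is mainly noise or dilution. The effect is confined to the DLQI change endpoints. The primary and key secondary results and the sample size are untouched.

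**What to change.** Add to SAP 4.4.8 (item 7), and mirror in Protocol 6.3.6: one unanswered DLQI item scores 0; if two or more are unanswered, the DLQI total is set to missing at that visit and handled by the plan's missing-data rule; an item marked as not relevant continues to score 0. The threshold of two is the one Appendix 5 prints for POEM, so the sponsor should confirm it against the DLQI's own scoring instructions before adopting it.

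If the device already makes every item mandatory, a sentence saying so would close the gap instead.

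The cost is one sentence in each document. The downside is that a few visits may become missing for the DLQI.

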6.3.7 Atopic Dermatitis Control Tool

The ADCT is a validated 6-item instrument with a 7-day recall period to measure AD disease control (Section 17.7 [Appendix 7]). This will be completed using an internet enabled device. The following domains are assessed: overall severity of symptoms, frequency of intense episodes of itching, severity of bother of itching, frequency of sleep impact, severity of daily activities impact, severity of mood or emotions impact. Each item is scored from 0 (none) to 4 (extreme). A total score of 7 or more points (derived by adding item scores) was identified during validation as an optimum threshold to identify patients whose AD is "not in control".

6.3.8 Hospital Anxiety and Depression Scale

The HADS is a validated 14-item PRO measure used to assess states of anxiety and depression over the past week. A copy of the HADS is included in Section 17.8 (Appendix 8). This will be completed using an internet-enabled device.

6.3.9 Numerical Rating Scale for Pruritus

The NRS for pruritus is an assessment tool that will be used to assess the patient's worst itch as a result of their AD in the previous 24 hours. This will be recorded daily, ideally in the morning, using an internet-enabled device with patients asked, "On a scale of "0" (no itch) to "10" (worst imaginable itch), how was your worst itch in the past 24 hours?" according to Section 17.9 (Appendix 9). Patients will additionally be asked to record NRS for 7 consecutive days immediately prior to Baseline. Sites will be encouraged to contact patients who have missed 2 consecutive e-diary entries to encourage patient compliance.

6.4 Safety and Tolerability Assessments

The Investigator will review results of safety assessments on a regular basis and the Sponsor must be kept fully informed of any clinically significant findings either at screening or subsequently during study conduct. All assessments will be performed at the timepoints outlined in the Schedule of Assessments (see Table 6-1, Table 6-2, Table 6-3 and Table 6-4).

6.4.1 Physical Examination

The Investigator will perform physical examinations throughout the study, consisting of assessment of general appearance, ears, eyes, nose, throat, mouth, neck, thyroid, skin, cardiovascular, respiratory, abdomen, neurological, musculoskeletal, lymph nodes and extremities.

6.4.2 Body Weight and Height

Body weight will be measured in kilograms (kg) and height in metres (m), with patients in light clothing and without shoes. Body weight will be assessed at Screening and during study treatment; height will be measured at Screening only.

Body mass index (BMI) will be calculated as follows:

$$BMI = Weight (kg) / Height (m)^2$$

6.4.3 Adverse Events

Investigators must carefully monitor patients for the occurrence of AEs, including clinical laboratory, vital signs and ECG variables. Assessments must be made of the seriousness, severity and relationship to the administration of study treatment (causality). Serious adverse events and specific AESI will require expedited reporting to the Sponsor. For details on definitions and reporting procedures see Section 8.1.

Adverse event assessments must be made by the Investigator or delegated to an appropriately trained and experienced physician. The Investigator is required to record the assessments in the eCRF and patient's medical notes. Any AEs already recorded and designated as "continuing" should be reviewed at each subsequent assessment.

During and following a patient's participation in this study, the Investigator must ensure that adequate medical care is provided to a patient for any AEs, including clinically significant laboratory values, related to the trial.

Adverse events and SAEs will be collected from the time of the patient signing the ICF until completion of the last visit. If an event that starts after the safety follow-up period is due to a late onset toxicity to study treatment, then it should be reported as an AE or SAE as applicable.

Investigators are not obligated to actively seek AE or SAE in former study patients. However, if the Investigator learns of any SAE, including a death, at any time after a patient's last visit and he/she considers the event to be reasonably related to the study treatment or study participation, the Sponsor should be notified.

6.4.4 Standard Laboratory Safety Tests

All standard safety laboratory parameters assessed will be evaluated centrally.

The standard laboratory safety tests consisting of haematology (full blood count [FBC]), clinical chemistry (electrolytes and non-fasting biochemistry) and urinalysis assessments defined in Table 6-5 will be performed throughout the study.

All WOCBP will also have a serum pregnancy test at Screening. Urine pregnancy tests will be performed pre-injection on IMP administration days, and at the early termination visit, Days 393 (Week 56), 449 (Week 64), and 477 (Week 68) of the safety follow-up period. These will be performed locally. If a urine pregnancy test result is positive, it must be confirmed by a serum pregnancy test.

For post-menopausal women only, a blood sample will also be taken at Screening for FSH.

Screening laboratory assessments may be repeated a maximum of once where initial results are in the Investigator's opinion, clinically significant and only provided the initial result is considered a temporary anomaly and there is a documented explanation as to the likely cause of the result (Section 4.6).

All laboratory reports should be reviewed, signed, and dated by a designated physician within 24 hours of receipt. These will be checked and verified by the Study Monitor during monitoring visits.

[figure not shown]
Table 6-5: Standard Laboratory SafetyTests

Category	Parameter
Haematology	WBCC and differentials, RBCC, RDW, Hb, HCT, nucleated red blood cells, platelet count, MCH, MCHC, MCV, and MPV
Clinical chemistry	Albumin, sodium, potassium, chloride, bicarbonate, urea, creatinine, glucose, calcium, phosphate, ALT, AST, GGT, LDH, alkaline phosphatase, total protein, iron, total bilirubin and CPK
Urinalysis	pH, protein, glucose, ketones and blood

ALT=alanine aminotransferase; AST=aspartate aminotransferase; CPK=creatine phosphokinase; GGT=gamma-glutamyl transferase; Hb=haemoglobin; HCT=haematocrit; LDH=lactate dehydrogenase; MCH=mean cell haemoglobin; MCHC=mean cell haemoglobin concentration; MCV=mean cell volume; MPV=mean platelet volume; RBCC=red blood cell count; RDW=red cell distribution width; WBCC=white blood cell count.

Assay methodology and procedures will be described in a laboratory manual to be finalised before the samples are collected. Samples will be shipped to and analysed by PPD Central Laboratory.

